Basic descriptive statistics for all outcome measures assessed both pre- and post-intervention. Internal consistency estimates, minimum and maximum scores, means and standard deviations are computed for each variable. To test for meaningful change over time, the change in mean score from Time 1 to Time 2 for each outcome measure was evaluated. Formal paired samples t-tests were conducted to test for statistical significance. However, given the small sample size and limited power, we also interpret Cohen's *d* as a more meaningful indicator of the magnitude of the observed effects.

Application Type
General Information
UNCC Personnel
Investigators Outside of UNCC
Conflict of Interest
Exemption
Research Location
Participants
Recruitment
Informed Consent Process
Study Methods and Procedures
Data Management
Benefits, Risks, Safety
Existing Data, Records, Specimens
Incentives and Costs
Study Attachments
PI Certification
Assignment
Review
All Pages

Application Type

Instructions

Before moving to the next page, carefully review the application type definitions listed below and then choose the application type that is appropriate for your research. This will populate the required protocol application pages for you to complete.

Application Type Definitions:

Initial Application: This application is for studies that will involve interaction, engagement, intervention, communication, etc. with human subjects. This may be direct or indirect (e.g., online surveys, use of survey panels, etc.) interactions.

Initial Application - Data Only: The application is for studies that will ONLY ever use data or biospecimens and NEVER have any direct interaction, engagement, intervention, communication, etc. with human subjects.

- Existing data refers to data you will receive or obtain from a source other than your study participant.
- Data obtained from secondary sources and not from the data collection procedures being proposed as part of this study.
- For example, if your study will involve existing data for secondary data analysis (e.g., student records, medical records, administrative data, etc.).
- Note, if you are conducting collaborative research and will be conducting data analysis for the larger collaboration, the IRB Reliance Agreement application type may be appropriate.

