Activities	 Obtain consent and/or assent  Perform research procedures  Administer study interventions or experiment  Obtain, use, or analyze identifiable or coded (has a study ID) data and/or specimens  Obtain, use, or analyze de-identified data and/or specimens  Other participant contact  Other responsibilities or roles
* Will the external institution and/or external collaborator defer review and oversight to the UNC Charlotte IRB?	Yes  No 
* Full legal name of external institution:	NA
* Federalwide Assurance (FWA) number from external Institution:	NA
* OHRP Registration Number of external IRB:	NA
* Contact Person at the external institution:	[name]
* Name, Title, Address, Phone, Email	[name]. [name]. [contact]. [contact]
* External institution signatory official:	Director of Human Subject Review Board at Rochester University
* Name, Title, Address, Phone, Email	[name], Administrator [contact]

Number of Participants

* 1. Total number of participants. 30

1.1 If this study will occur at multiple Research Locations (as listed on the Research Locations page), please specify the number of participants at each location/site. If this study is not occurring at multiple Research Locations state "Not Applicable."

All study activities will happen virtually using a zoom videoconference platform with HIPPA compliance

2. If the Total Number of participants listed above (question #1) includes multiple groups or cohorts of participants, please explain the number of participants for each group.

Cohort 1 = 10 participants will engage in a demonstration test of the program to further refine the content and design of the program in Spanish

Cohort 2 = 20 participants will engage in a pilot test for program to finalize the final version of the Spanish program.

Vulnerable or Select Populations

3. Do you have specific plans to include participants from these vulnerable or select populations? If so, check all that apply

☐ Children (under the age of majority for their location)

☒ Non-English-speaking

☐ Patients (i.e., have a specific disease, disorder or condition regardless of where they receive their healthcare)

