materials; each initial meeting will focus on one workshop session and feedback will be obtained on: how content is presented; appropriateness of examples and action plans; how to increase social connectedness -particularly with family members – within the context of that workshop's focus. The CAB will also review the program Website that is in English, and make recommendations to make it user-friendly for Latino caregivers. The CAB will recommend ways to use this website to increase social connectedness. CAB members need to identify as Latino, be bilingual, and have the necessary time and skills to participate. To meet Aim 2 (Stage 1B trial), based on this feedback, a preliminary adapted version will be tested in an Stage 1B trial (pre- post design). We will recruit 20 Latino caregivers and all will receive the intervention (with n=10 in each group, run sequentially). We will make refinements (if needed) based on participant and CAB feedback between the first and second group. We will collect qualitative and quantitative data with several metrics (described below). Caregivers need to be men and women, 45 years and older, who identify as primary caregivers of a PLWD with whom they co-reside or live close by. A stress rating will be used so that at least a moderate level of stress related to caregiving is endorsed. Willingness to complete interviews and surveys and provide feedback are also necessary. To address Aim 3, (mechanisms) we will assess changes in loneliness and social support and anticipate that Latino caregivers who demonstrate decreases in loneliness and increases in social support will experience lower stress levels, burden and depression.

6. Analytic Plans: We will collect qualitative and descriptive quantitative data using mixed methods: 1. Individual semi-structured interviews with members of the CAB to ask them about caregivers' needs, supportive services, cultural views and normative expectations about care. 2. Data from Focus Group participants on feasibility and acceptability of the adaptation and refinement. 3. Descriptive pre-post data from the early developmental trial (20 caregivers). Data Analytics.

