- C) What are the main sources of informal and formal support available for Latino caregivers providing care to PLVD in the community? **SPANISH:** Indicar los servicios de apoyo informal y formal disponibles para Latinos que cuidan de familiares con demencia en la comunidad.
- D) What are the main cultural barriers/opportunities for Latino caregivers providing care to PLVD in the community? **SPANISH:** Indicar los aspectos culturales que son barreras o facilitadores para Latinos que cuidan a familiares con demencia en la comunidad.

- 2. Focus Group to included program facilitators and consented participants in the pilot demonstration to report on the feasibility and acceptability of the adaptation:**

Sample questions (English/Spanish):

- A) What are the main difficulties Latino caregivers may encounter with the Caring Together educational program regarding content topics, activities, structure, design, resources, and use of technology? **SPANISH:** Indicar las dificultades con diversos aspectos del programa para Latinos que cuidan de familiares con demencia (sobre el contenido, actividades, estructura, diseño, recursos y uso de la tecnología)?
- B) What are the expected levels of satisfaction and acceptability of the Caring Together educational program among Latino caregivers of PLVD in the community? **SPANISH:** Indicar las expectativas de aceptación y satisfacción con el programa para Latinos que cuidan de familiares con demencia en la comunidad.
- C) What are the main values recognized/ignored by the Caring Together educational program for Latino caregivers of PLVD in the community? **SPANISH:** Indicar los valores culturales adoptados/ignorados por el programa para Latinos que cuidan de familiares con demencia.

3. Descriptive pre-post data from the early developmental trial (20 caregivers). Measures to assess the feasibility and acceptability of the program by participants in the pilot study.

Sample questions (English/Spanish):

- A) Percentage of Completed action plans. **SPANISH:** Indicar porcentaje de Latinos que completan el plan de acción del programa.
- B) Likert six-point self-report scales for: program satisfaction; new skills learned; usefulness of skills; helpfulness of skills; likelihood of using skills in future. **SPANISH:** Uso de escalas de tipo Likert para medir los niveles de satisfacción sobre el programa, el uso y utilidad de las habilidades y destrezas aprendidas, las estrategias y uso anticipado de las mismas.

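### Enrolment is 30 (10 + 20) in one section and 20 (10 + 10) in another, and the pre-post analysis does not say which cohort or program version it covers

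*Combined protocol and SAP*

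**What the plan says.** **Size and structure, IRB application.** Number of Participants, question 1, reads "Total number of participants. 30". Question 2 splits this into two cohorts. The first is described as "Cohort 1 = 10 participants will engage in a demonstration test of the program to further refine the content and design of the program", the second as "Cohort 2 = 20 participants will engage in a pilot test for program to finalize the final version of the Spanish program".

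**Size and structure, attachments.** In the grant application (Research Design, item 5, Study Design) the text is "We will recruit 20 Latino caregivers and all will receive the intervention (with n=10 in each group, run sequentially". Item 6 of the same section, Analytic Plans, and item 3 of the Project 9 Measures file both refer to "Descriptive pre-post data from the early developmental trial (20 caregivers". Both files are attachments to the same IRB submission, and neither is marked as superseded.

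**Revision of the program.** Study Design adds: "We will make refinements (if needed) based on participant and CAB feedback between the first and second group".

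**Analysis.** The Data Analysis Plan says that "the change in mean score from Time 1 to Time 2 for each outcome measure was evaluated", and then "Formal paired samples t-tests were conducted to test for statistical significance". It adds Cohen's d as an indicator of magnitude. Study Methods and Procedures, question 6, adds bivariate and basic multivariate pre-post analyses adjusted for sociodemographic variables. None of these sections names a cohort, a group or a program version.

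**The concern.** There are two linked problems. First, one study cannot have both sizes. The two descriptions also differ in structure: the second cohort is 20 in one and 10 in the other.

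Second, the first group serves partly to improve the program before the second group starts. If content changes, the two groups receive different versions. An analysis that is silent on cohort can then yield one mean change that averages over versions. It also leaves the choice of 10, 20 or 30 analysed caregivers open until results are known.

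The study is exploratory and states no quantitative hypothesis. However, the application also presents it as an early look at efficacy, and the grant describes it as leading to a Stage II proposal. The Data Analysis Plan treats Cohen's d as more informative than the p-value, so readers need to know whose d it is.

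**Working it through.** **1. Do the totals reproduce?** IRB application: 10 + 20 = 30. Grant application: 10 + 10 = 20. Each is consistent within its own section, so this is not a slip in addition. The totals differ by 10 people.

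**2. Can they be reconciled?** The most favourable reading is that the grant's 20 are the IRB application's Cohort 2 only. That does not fit well, because Study Design presents the 20 as everyone recruited. If it were right, Cohort 2 would itself be two groups of 10 with possible refinement between them, after Cohort 1's own refinement step. That would allow up to three versions.

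**3. Precision at each possible n.** The documents give no alpha, sidedness, power, effect size, SD or dropout rate, so neither total can be derived from a power calculation. Assume two-sided alpha 0.05 and complete pre and post data. In units of the SD of change, the half-width of the 95% interval is t(0.975, n − 1)/√n:

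| n | Half-width | Paired effect detectable with 80% power (noncentral t) | Power at a paired effect of 0.5 |
|---|---|---|---|
| 10 | 2.262/√10 = 0.72 | 1.00 | 29% |
| 20 | 2.093/√20 = 0.47 | 0.66 | 56% |
| 30 | 2.045/√30 = 0.37 | 0.53 | 75% |

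**4. What pooling would do.** The effects here are assumed, with SD of change 1 within each version. The pooled mean is (n1·d1 + n2·d2)/(n1 + n2).

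- First version 0.2, revised version 0.5: (10·0.2 + 10·0.5)/20 = 0.35, or (10·0.2 + 20·0.5)/30 = 0.40.
- First version 0.2, revised version 0.8: 0.50 under 10 + 10, or 0.60 under 10 + 20.
- Both versions 0.5: 0.50 under either structure, so nothing is lost.

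**5. Is the second group alone a better estimate of the revised version?** Compare root-mean-square error for the revised version's effect.

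- Effects 0.2 and 0.5, 10 + 10: pooled √(1/20 + 0.15²) = 0.27; second group alone √(1/10) = 0.32.
- Effects 0.2 and 0.5, 10 + 20: pooled √(1/30 + 0.10²) = 0.21; second group alone √(1/20) = 0.22.
- Effects 0.2 and 0.8, 10 + 10: pooled √(1/20 + 0.30²) = 0.37 against 0.32.
- Effects 0.2 and 0.8, 10 + 20: pooled √(1/30 + 0.20²) = 0.27 against 0.22.

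Let g be the gap between versions. The pooled bias is g/2 under 10 + 10 and g/3 under 10 + 20. Pooling has the smaller error when g²/4 < 1/10 − 1/20, so g < 0.45 SD, or when g²/9 < 1/20 − 1/30, so g < 0.39 SD.

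**6. Could the data show that versions are equivalent?** A difference in change between cohorts must be about 1.3 SD (10 against 10) or 1.1 SD (10 against 20) to be detected with 80% power. A non-significant difference would therefore not show that the versions are equivalent.

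**The case against.** A reader might infer more than the documents support.

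- **That one paired t-test is planned.** The plan has paired t-tests for each outcome, read with Cohen's d, and adjusted analyses besides.
- **That the plan pools the cohorts.** It never says so. The defect is silence about the analysis set. The IRB application distinguishes a demonstration test from a pilot test, so the 20 caregivers in the measures file could mean Cohort 2 alone.
- **That the result describes no single version.** This needs both pooling and an actual change of content. Study Design makes refinement conditional. The IRB application gives refinement as Cohort 1's purpose, which makes change likely but not certain.
- **That the second cohort receives the final version and must be the main estimate.** Cohort 2's own stated purpose is to finalize the program, so its version may still change. Step 5 shows that pooling can be the more accurate choice when versions differ modestly.

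The defence also notes that this is a Stage I adaptation pilot, where refining between groups is the purpose, and that the plan already concedes small numbers and limited power. No section says that the pre-post estimate will size or gate the Stage II trial.

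All of this stands and limits the point on version mixing. None of it resolves 30 against 20 or says who enters the analysis.

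**Conclusion.** The conflict in enrolment and cohort structure is certain on the text: 30 as 10 + 20 against 20 as 10 + 10. At least one statement of the sample size is wrong as written and must be corrected.

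The version problem holds in a conditional form: if content changes and one overall estimate is reported, that estimate may mix versions. How far it would be off is unknown. On the assumed effects in step 4, the pooled mean differs from the revised version's effect by between 0 and 0.30 SD. Even the largest of these is smaller than the half-width of 0.72 SD at n = 10.

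The half-widths need only the analysed n and complete pairs. The detectable effects also assume 80% power, which the documents do not state. Confining the main estimate to the second cohort, or barring pooling after any edit, is a trade-off rather than a requirement.

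**What to change.** 1. State one total and one cohort structure, and correct the Number of Participants section, Study Design, Analytic Plans and the measures file to match.
2. In the Data Analysis Plan, name before any outcome data are seen which cohort or cohorts enter the paired and adjusted analyses.
3. Report mean change and Cohen's d with 95% confidence intervals by cohort, alongside any pooled estimate, each labelled by the program version received.
4. Keep a dated record of program changes made between groups, so that a reader can judge whether they are wording edits or changes of content.

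This needs wording and reporting only, with no extra participants. The cost is wider by-cohort intervals: 0.72 SD for a cohort of 10, against 0.47 or 0.37 SD for 20 or 30 analysed together. The report should say plainly that similar results in the two cohorts are not evidence that the versions are equivalent.

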
Assessment and Cuidando Juntos Sessions:

Once informed consent is obtained, participants will be contacted regarding completion of the first assessment survey (pre-assessment). Once the consent form and first survey is completed each participant will be assigned to a group led by one of the trained facilitators based on the indicated availability. Once assigned to a group, participants will be emailed their zoom invitation from the facilitator. After completing the Cuidando Juntos program, participants will be emailed a link to a post assessment Qualtrics survey. Participants will also be required to indicate their consent on each electronic survey (pre and post) prior to accessing any survey questions. Participants who do not indicate their agreement to proceed with each electronic survey will not be directed to respond to any survey questions and will also be asked if they would like to withdraw from the study and receive no further contact from the research team. Participants will also be asked to participate in a focus group and answer semi-structured interview questions after completing the Cuidando Juntos program. Participants will indicate their consent to participate in the semi-structured interview on the initial consent form and will also be emailed a link to an electronic survey administered via Qualtrics and will be required to indicate their consent to participate in the semi-structured interview focus group prior to being emailed the link to the Zoom meeting. Participants who do not indicate their agreement to participate in the focus group will also be asked if they would like to withdraw from the study and receive no further contact from the research team. Participants who indicate they would like to completely withdraw will no longer be contacted by members of the research team. Participants can choose to withdraw from the study at any time.

Confidentiality and Program Access:

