We will assess caregivers approximately one week prior to the training one week after completing the program. These measures are standard in the caregiving literature, and focus on both the positive and potential negative aspects of caregiving. At each occasion, they would require approximately an hour to complete. In addition to these assessments, caregivers will attend 6 weekly sessions to complete the program. Participants will also answer semi-structure interview questions as part of focus group discussions after completing the six week sessions.

The estimated duration of participation is approximately 2 months.

After qualifying participants are consented they will be assigned to participate in the "Cuidando Juntos" program group. Once assigned, participants will complete a pre assessment survey approximately one week before beginning the program. The pre-assessment survey will be completed virtually using Qualtrics and will take approximately 40 minutes to complete. Participants will then complete the six weekly "Cuidando Juntos" program sessions, each lasting two hours. One week after completion of the sessions participants will complete a post assessment survey virtually using Qualtrics, which will take approximately 40 minutes to complete. Between one and two weeks after completing the program sessions, all participants in the program group will be invited to participate in a virtual focus group via HIPAA zoom platform. Participants will be ask to respond to semi-structured questions about the program during the focus group. The group will be lead by a bilingual/bicultural member of the research team. The focus group will last two hours. Total participation for the duration of the study will be approximately ten week for participants.

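### Declining the focus group prompts an offer to leave the whole study at a point when the post-assessment may still be outstanding, so some Time 2 records can be lost or answered after the group discussion

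*Combined protocol and SAP*

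**What the plan says.** Three procedural statements in the IRB application bear on this point, and one statement in the analysis plan.

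- **Consequence of declining (Assessment and Cuidando Juntos Sessions).** The rule covers caregivers who, in its words, "do not indicate their agreement to participate in the focus group will also be asked if they would like to withdraw from the study". The offer is one of ending all contact. The text continues: "Participants who indicate they would like to completely withdraw will no longer be contacted by members of the research team".
- **Access to the focus group (same section).** Participants are "required to indicate their consent to participate in the semi-structured interview focus group prior to being emailed the link to the Zoom meeting". No other condition on the link is stated.
- **Timing (Duration of participation).** "One week after completion of the sessions participants will complete a post assessment survey virtually using Qualtrics". For the focus group: "Between one and two weeks after completing the program sessions, all participants in the program group will be invited" to a virtual meeting. "The focus group will last two hours", the same length as a program session.
- **Analysis (Data Analysis Plan).** Change from Time 1 to Time 2 is assessed by mean change, paired t-tests and Cohen's d. No rule is given there for missing or late Time 2 records.

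**The concern.** Time 2 is the study's only follow-up, and every paired comparison needs it. Two features of the schedule put it at avoidable risk.

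First, a caregiver who has no time for a two-hour meeting, but would have filled in a survey, is asked whether to leave the study altogether. If that caregiver accepts with the survey unanswered, contact stops and the pair is lost. A refusal of one optional component has then cost the outcome data.

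Second, a caregiver who agrees to the group but has not answered the survey may attend first. The group discusses difficulties, satisfaction and cultural fit. According to the measures appendix, it also includes program facilitators. Loneliness and social-network answers given afterwards no longer reflect the six sessions alone. The same would hold for satisfaction ratings if they are collected in that survey.

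**Working it through.** The plan gives no power, attrition or effect-size figure, so there is nothing of its own to reproduce. The check is a comparison of timings, followed by an illustration of scale.

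**Timings, counted from the last session**

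| Event | Time | Stated condition |
|---|---|---|
| Post-assessment link emailed | after the program, day not given | none |
| Post-assessment completed | week 1 | no closing date |
| Focus-group invitations | week 1 to week 2 | none |
| Zoom link for the group | after focus-group consent | focus-group consent only |

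The gap between the Time 2 time point and the first permitted invitation is 1 − 1 = 0 weeks. No section requires Time 2 to be submitted before the invitation, the consent survey or the meeting. The link timing rests on "After completing the Cuidando Juntos program, participants will be emailed a link to a post assessment Qualtrics survey", which allows the survey to arrive before week 1. The coincidence is therefore exact for the week-1 completion point, but not necessarily for the email.

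**Who is exposed.** A lost record needs three things in one caregiver: Time 2 outstanding, the group declined, and the withdrawal offer accepted. A late record needs two: Time 2 outstanding and the group attended.

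**Scale of loss.** The number lost, L, is assumed to be 0 to 5. The number enrolled, N, is 20 in the grant application (Study Design) and 30 in the IRB application (Number of Participants). The standard error of a mean change is multiplied by √(N / (N − L)):

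- N = 20, L = 0: 1.00. L = 3: √(20/17) = 1.085. L = 5: √(20/15) = 1.155.
- N = 30, L = 0: 1.00. L = 3: √(30/27) = 1.054. L = 5: √(30/25) = 1.095.

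**Power, for orientation only.** This uses the noncentral t distribution for a paired test. Assumed inputs are two-sided alpha 0.05 and an effect of 0.5 SD of the change score. Power is 0.56 with 20 pairs and 0.44 with 15. The effect detectable with 80% power rises from 0.66 to 0.78 SD.

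**Selection bias.** If the mean change of those lost differs from that of completers by D SD, the completer mean is off by (L/N) × D. With N = 20, L = 0 to 5 and D up to 1.0 in size, this runs from 0 to (5/20) × 1.0 = 0.25 SD. The sign of D is not known.

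**The case against.** The strongest reply is that the text does not expel anyone. A reader might infer that refusing the focus group ends participation. The documents do not support that: the caregiver is asked, and only those who choose complete withdrawal lose contact. Nothing says that data already given are discarded. The same question follows refusal of the pre or post survey, so it reads as a uniform voluntariness step. All of this stands and limits the point to caregivers with Time 2 outstanding. It does not remove it. Refusing the post-assessment is itself a refusal of Time 2, whereas refusing the focus group is not, so there the prompt puts at risk data the caregiver had not declined to give.

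The intended order is also Time 2 first, and a consent step must follow the invitation before anyone meets. That too stands: answering after the group is permitted by silence, not planned.

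On size, any specific number of losses is an assumption. If each of the three conditions had probability 0.3, the expected loss would be 20 × 0.3³ = 0.54 caregivers, so the range must include 0. Some who accept withdrawal might never have answered anyway.

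Two further inferences do not hold. One is that losing burdened caregivers tilts results toward benefit. Entry requires elevated stress, so the most burdened may have the most room to improve, and their loss could shrink the observed change. The other is that the group adds 2/12 = 17% to program contact. It is an evaluation discussion led by a research-team member, not a seventh session.

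Finally, this is an exploratory pilot whose surveys were still in development, and the consent form is not in the copy reviewed. If those materials already set the order, the timing half of the point falls away.

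**Conclusion.** The point holds in a limited form. As written, the procedures let a caregiver with an outstanding Time 2 survey be offered study withdrawal for declining a separate component, or attend the group before answering. Both are avoidable.

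The frequency cannot be derived from the documents. With 0 to 5 records lost (assumed), standard errors rise by 0% to about 15% at N = 20 and by 0% to about 10% at N = 30. Any selection bias could go in either direction. The documents do not show that losses will occur, that they would favour the program, or that declining the group removes anyone automatically. The change is worth making because Time 2 is the only follow-up, precision is already described as limited, and the remedy is small.

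**What to change.** 1. **Order.** Send the focus-group consent survey and Zoom link to a caregiver only after that caregiver's post-assessment is submitted or, failing that, shortly before the group meets. Do not close Time 2 at that point, because a hard cut-off would turn late answers into missing ones. Record the Time 2 date relative to the focus group, so that answers given afterwards can be flagged and left out in a sensitivity analysis.
2. **Wording.** After a focus-group refusal, replace the study-withdrawal question with a statement that the caregiver remains in the study and will still receive the post-assessment. Leave the general right to withdraw at any time unchanged.

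The cost is one gate on a Qualtrics consent step that already exists, one reworded prompt and one date comparison. No new data collection from participants is needed. The surveys and focus-group questions were due to go to the IRB before any participant was contacted, so the change could travel with them. The downside is that some focus-group links go out a few days later.
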